#### **Specific Aim #1: To determine safety and tolerability of Losartan when used for treatment of an acute grade II or III hamstring strain.**

*Hypothesis 1a:* Use of Losartan will have an acceptable adverse event profile that is comparable to placebo. To test this hypothesis we will monitor adverse and serious adverse events throughout the duration of the study.

*Hypothesis 1b:* The side effect profile of Losartan will be comparable to placebo. To test this hypothesis we will monitor subject complaints, symptoms, hypotension, and laboratory values.

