**Figure 1 – Flow Chart for Study Design**

### **3.2 Allocation to treatment**

Subjects will be randomized in a 1:1 ratio to either treatment with Losartan or placebo. Both groups will otherwise undergo the same standard of care rehabilitation for treatment of an acute hamstring injury. The randomization list will be generated using a random number generator. An equal number of subjects will be allocated to each group in random block sizes of two and four. Group assignments will be placed in sequentially numbered opaque envelopes, which will be opened by the Project Coordinator at each site once the participant has agreed to participate in the study and baseline testing has been completed to confirm subject eligibility. Thus the treatment allocation will be concealed from the Project Coordinator and others responsible for recruitment. To minimize bias throughout the study, both the subject and individuals responsible for outcome measure collection/analysis will remain blinded to the group assignment.

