The severity of an adverse event will be determined by the study medical director based on the criteria stated in section 8.1. Additionally, the medical director will assign the event a grade of mild, moderate, or severe. If it becomes medically necessary to withdraw the subject from the study, the study medication will be discontinued. The subject will be followed clinically until the adverse event or abnormal test findings felt to be associated with the study drug resolves or stabilizes at a level acceptable to the Sponsor-Investigator. This follow-up will include assessment of vital signs, physical examination and assessment of blood work. Follow-up blood work will be performed 4-6 weeks ( $\pm 3$  days) after discontinuing medication to ensure that lab values have returned to normal ranges after discontinuation of the study medication. The subject will be treated for any medication related problems as clinically appropriate. Information from this appointment will be documented in the subject's case file. The patient will be terminated from the study, and will not complete any further follow-up appointments for the study. Subjects that are terminated from participation in the study due to an adverse event will be replaced by recruitment of another subject.

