## **9.2        Sample size determination**

With an approved sample size of 20 patients (10 in each group), we will not have enough statistical power to detect statistically significant differences in clinical measures between the Losartan and placebo groups. Therefore the objective of this phase 1 trial is to observe trends by group and estimate effect sizes that can be used to inform power calculations in future clinical trials.

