## **9.5 Safety analysis**

To assess safety, vital signs will be monitored daily and we will also monitor the frequency abnormal lab values as well as adverse and serious adverse events during period of active intervention as well as throughout the subjects' participation in the study. To assess the side effect profile of Losartan in this population, we will monitor the frequency of subject complaints, symptoms (dizziness, new fatigue, peripheral edema, urinary symptoms) and laboratory measures of liver and renal function, hemoglobin and hematocrit counts and serum potassium and uric acid levels. The frequency of abnormal lab values, adverse and serious adverse events and side effects will be monitored separately for the Losartan and placebo control groups. Differences between groups will be assessed using Fisher exact tests.

Any deviations from the previously described statistical plan will be described and justified in a protocol amendment and/or in the final report submitted to the IND application.

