#### **13.2 Sponsor-Investigator discontinuation of the clinical research study**

Adverse events will be continuously monitored by the Data and Safety Monitoring Committee. If the number or severity adverse events are greater than the expected adverse events associated with Losartan, the DSMC will make the recommendation for termination or modification of study.

Any modifications in the study protocol will be submitted for review and approval by the IRB before the modification is implemented. Modifications in the study protocol will be communicated to all study sites in writing. Subjects will be notified of modifications in the study protocol and if appropriate will be re-consented for their continued participation in the modified study.

If the DSMC recommends termination of the study due to safety concerns, the IRB and all study sites will be notified immediately by the study principal investigator, followed by notification in writing. Enrolled subjects will be notified of the study termination by the site principal investigator by phone, and also in writing. If subjects are taking study medication at the time of study termination, they will be instructed to discontinue the study medication as clinically appropriate.

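### The Aim 1 safety comparison never uses the mild/moderate/severe grade, so a difference in severity at similar incidence is not examined

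*Combined protocol and SAP*

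**What the plan says.** - **Aim.** Safety and tolerability is Specific Aim 1 and comes first under primary endpoints in 9.1.1. Hypothesis 1a reads: "Use of Losartan will have an acceptable adverse event profile that is comparable to placebo".
- **Analysis.** Sections 9.1.1 and 9.5 follow the frequency, by arm, of abnormal laboratory values, adverse and serious adverse events and side effects. The named symptoms are dizziness, new fatigue, peripheral edema and urinary symptoms. Section 9.5 then states: "Differences between groups will be assessed using Fisher exact tests". No significance level, sidedness or unit of count (subject or event) is given.
- **Grade.** Section 8.4 says: "Additionally, the medical director will assign the event a grade of mild, moderate, or severe". It refers to section 8.1 for severity criteria, but 8.1 defines seriousness, life-threatening and unexpected reactions, not the three grades. Section 8.2.2.2 has severity in its title and sets no grade.
- **Use of severity.** Section 13.2 sets the trigger for a monitoring committee recommendation: "If the number or severity adverse events are greater than the expected adverse events associated with Losartan".
- **Size.** Section 9.2: "With an approved sample size of 20 patients (10 in each group"), and "we will not have enough statistical power to detect statistically significant differences in clinical measures". It adds that "the objective of this phase 1 trial is to observe trends by group and estimate effect sizes".

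**The concern.** The plan collects a grade, treats severity as a reason to stop or modify the trial, and then leaves the grade out of the primary safety summary. The serious/non-serious split does not stand in for it. Seriousness in 8.1 covers death, life-threatening reactions, hospitalisation, incapacity, birth defect and comparable important medical events. Severe dizziness or fatigue that meets none of these is counted exactly like a mild episode.

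What is at stake is the description of tolerability. Suppose the arms have similar numbers of subjects with events, but those on losartan are moderate or severe and those on placebo mild. The planned tables would look the same for both arms, and a later trial would be designed without that information.

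**Working it through.** **Nothing to reproduce.** The 20 subjects are an approved number with no effect size, significance level or power target behind it.

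**Inputs.** From the documents: 10 per arm (9.2), 1:1 allocation (3.2), Fisher exact tests (9.5). Assumed: two-sided 0.05; one score per subject, the worst grade (none, mild, moderate, severe); all incidences and grade distributions.

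**Step 1: what Fisher can detect at 10 v 10.** For 5 v 0 subjects, p = 2 × C(10,5) / C(20,5) = 2 × 252 / 15,504 = 0.033. For 4 v 0, p = 2 × 210 / 4,845 = 0.087. The smallest significant splits are 5 v 0, 7 v 1, 8 v 2, 9 v 3 and 10 v 4. Power is the sum of Bin(x; 10, p1) × Bin(y; 10, p2) over all splits with p ≤ 0.05. This gives 25% for 60% v 20% and 12% for 60% v 30%.

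**Step 2: equal incidence, worse grades on losartan.** Distributions are none/mild/moderate/severe in percent. Fisher columns are exact enumeration; the rank test is an exact conditional Wilcoxon test, 20,000 simulated trials per row.

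| Placebo | Losartan | Fisher, any event | Fisher, moderate or worse | Fisher, severe | Wilcoxon, worst grade |
|---|---|---|---|---|---|
| 60/30/8/2 | 60/5/15/20 | 1.3% | 10% | 3% | 6% |
| 40/45/10/5 | 40/10/25/25 | 1.3% | 20% | 5% | 14% |
| 40/50/10/0 | 40/10/35/15 | 1.3% | 30% | 1% | 16% |
| 40/50/8/2 | 40/5/25/30 | 1.3% | 38% | 13% | 21% |
| 40/60/0/0 | 40/0/0/60 | 1.3% | 83% | 83% | 33% |
| 20/60/15/5 | 20/20/30/30 | 0.8% | 25% | 9% | 28% |
| 10/70/15/5 | 10/20/35/35 | 0.1% | 43% | 16% | 51% |

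Fisher on any event is blind to these shifts by construction: its rejection rate is just its type I error. In the third row a Fisher test on the full four-level table rejects in about 46%.

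**Step 3: incidence and grade both worse.**
- Placebo 70/20/7/3, losartan 40/20/20/20: Fisher on any event 12%, on moderate-or-worse 15%, Wilcoxon 29%.
- Proportional odds, placebo incidence 60% (odds 1.5). Odds ratios 3, 5 and 8 give losartan odds 4.5, 7.5 and 12, so incidences 82%, 88% and 92%. Fisher on any event rejects in 7%, 13% and 19%. The rank test rejects in roughly 20–23%, 39–43% and 60–63%, depending on the assumed placebo grade split.

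**Step 4: false positives.** With 40/40/15/5 in both arms the rank test rejects in 3.3%.

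**Reading.** Either way of using the grade adds information. Neither dominates: moderate-or-worse does better in five of the seven pure severity shifts, and the rank test does better when incidence moves too or nearly everyone has an event.

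**The case against.** The strongest reply is that this is a 10-per-arm phase 1 trial that disclaims power and sets out to describe trends, so judging its safety tables by rejection rates misses the purpose. Much of that stands: sample size is the main limit, and at equal incidence most assumed severity shifts would be missed with the grade as well. But a trial meant to show trends and effect sizes has reason to show this one, and the grade is already provided for.

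Four stronger readings are tempting and are not supported:
- *Fisher is the wrong test.* It is not. Applied to moderate-or-worse it often beats the rank test (30% v 16% in the third row), and on the full grade table it does better still. What is missing is a tabulation.
- *The plan reduces events to yes/no.* Section 9.5 says frequency, fixes no unit, names several categories and does not restrict Fisher tests to 2 × 2 tables. Subjects with and without an event is the natural reading, but an inference.
- *Severity is ignored.* Serious events are compared separately and the monitoring committee is to consider severity. The omission is in the between-arm analysis.
- *A non-significant test will be declared comparable.* No such decision rule is written.

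One caution also stands. The grading sentence sits in the section on withdrawal for adverse events, so it is not certain that every event is to be graded.

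**Conclusion.** The point holds as a gap in the primary safety summary. A grade is assigned and severity is relevant to stopping, but 9.1.1 and 9.5 neither summarise nor compare it, so a severity difference at similar incidence is not examined. A reader might infer that the choice of Fisher tests is what would hide a harsher profile, or that an ordinal test would reveal it. The figures do not bear that out: at equal incidence the rank test moves the rejection rate from about 1% to between 6% and 51%, and exceeds 33% only when 90% of subjects have an event. The gap does not invalidate the safety analysis; closing it is a worthwhile, nearly free improvement.

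That the grade is left out follows from the text. Every rejection rate depends on assumed incidences, grade distributions and a two-sided 0.05 level, none of which the documents give.

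**What to change.** 1. Define mild, moderate and severe (8.1 does not), and state in 8.2.2.2 or 8.4 that the grade applies to every adverse event, not only those leading to withdrawal.
2. In 9.1.1 (Aim 1) and 9.5, tabulate subjects by worst grade (none, mild, moderate, severe) and arm, for the dosing period and for the whole study.
3. Report the proportions with a moderate-or-worse event and with a severe event, with the between-arm difference, exact 95% confidence intervals and Fisher tests.
4. Add, as supportive, an exact Wilcoxon comparison of worst grade, with the estimated probability that a losartan subject has a worse grade than a placebo subject and its confidence interval.
5. Keep the existing frequency comparisons and Fisher tests, including those for serious adverse events, and state that subjects are the unit of count.

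Cost: grade definitions, some analysis wording, one more table and a few extra descriptive comparisons. If every event is graded as 8.4 suggests, no new data are needed; if only withdrawals were to be graded, the medical director grades the remaining events too. The added tests are descriptive and should be labelled so.

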## **9.6        Interim analysis**

No interim analysis is planned.

## **9.7        Data and Safety Monitoring Committee**

### **9.7.1 Type of Monitoring Body**

The data and safety monitoring activities for this phase 1 clinical trial will be under the oversight of a Data and Safety Monitoring Committee (DSMC) consisting of the principal investigators from each site, the study statistician, and other appointed investigators. The goals of this DSMC are to ensure the safety of the study participants, integrity of the data and the validity of the study results. The data and safety monitoring activities will focus on safety of the study participants; performance of the investigative team with respect to participant recruitment, retention and follow-up, adherence to the protocol, and quality of the data; and to evaluate if the study should continue.

### **9.7.2 Membership of the Data and Safety Monitoring Committee**

The DSMC will be comprised of the principal investigators from each site, study statistician, and other appointed investigators. A DSMC member will be obligated to bring an issue of any potential conflict of interest to the attention of the full DSMC for open discussion and resolution.

[name] will act as the committee chairperson. He will be responsible for overseeing the meetings and working with the project coordinator at the coordinating site to develop the agenda and summarize the meeting.

[name] will serve as the Safety Officer for this study. She will be the contact person for serious adverse event reporting and study safety issues. [name] will review of events that might impact the safety of participants and/or the safety of the data for this study.

### **9.7.3 Responsibilities of the Data and Safety Monitoring Committee**

The DSMC will be responsible for assuring that subjects are not exposed to unnecessary or unreasonable risks and that the investigator conducts the clinical trial according to the highest scientific and ethical standards.

Initially, in the planning and development phase of this study, the DSMC will review and make recommendations regarding the research protocol, informed

consent documents, quality control plans, and plans for data and safety monitoring prior to the study initiation.

Once the study is implemented, ongoing responsibilities of the DSMC will be to:

- Evaluate the progress of trial, including periodic assessments of data quality and timeliness; participant recruitment, accrual and retention; participant risk versus benefit ratio; performance of the trial site; and other factors that can affect study outcome;
- Consider the impact of factors external to the study when new information, such as scientific or surgical developments become available and may affect the safety of participants, their willingness to participate in the study, or the conduct of the trial;
- Review study performance, make recommendations and assist in the resolution of problems reported by the investigators;
- Protect the safety and privacy of study participants;
- Report on the safety and scientific progress of the trial;
- Make recommendations concerning continuation, termination, or other modifications of the trial based on the observed adverse effects of the treatment under study;
- Ensure data integrity;
- Ensure confidentiality of the trial data and the results of monitoring;
- Assist by commenting on any problems with study conduct, enrollment, sample size, statistics, and/or data collection; and
- Review and evaluate requests for protocol modifications after the trial begins to evaluate whether the study should continue as approved or undergo a protocol modification.

## **9.7.4 Data and Safety Monitoring Committee Processes and Procedures**

### **9.7.4.1 Meetings of the Data and Safety Monitoring Committee**

The DSMC will meet at designated intervals to review accumulated data on safety. Meetings will be convened as conference calls or in person, although it is recommended that the initial meeting and meetings to discuss interim analyses be face-to-face. An emergency meeting of the DSMC will be called at any time by the investigators should questions of patient safety arise. Notes and minutes of each meeting of the DSMC will be recorded and stored in the study regulatory files.

Each meeting will include a recommendation to continue or to terminate the study made by DSMC majority or unanimous vote. Should the DSMC decide to issue a termination recommendation, the full vote of the DSMC will be required. In the event of a split vote, the majority vote will rule and a minority report should

be appended. In the event of a 50-50 split vote, the DSMC Chairperson will provide the tie breaker.

#### **9.7.4.2 Interim Analyses**

No interim analyses are planned. However, any data reviewed by the DSMC will be limited to as small a group as possible. Data files to be used for review will have undergone established editing procedures to the extent possible.

#### **9.7.4.3 Termination of Study**

A recommendation to terminate the study may be made by the DSMC at any time.

#### **9.7.4.4 Confidentiality**

All materials, discussions, and proceedings of the DSMC will be completely confidential. Members and other participants in DSMC meetings will be expected to maintain confidentiality at all times.

### **10. Quality Control and Quality Assurance:**

Independent monitoring of the clinical study for protocol and GCP compliance will be conducted periodically (i.e., at a minimum of annually) by qualified staff of the Education and Compliance Office – Human Subject Research, Research Conduct and Compliance Office, University of Pittsburgh.

The Sponsor-Investigator and the University of Pittsburgh and UPMC will permit direct access of the study monitors and appropriate regulatory authorities to the study data and to the corresponding source data and documents to verify the accuracy of this data.

Data integrity and credibility of the study are dependent on strict adherence to the protocol, obtaining complete follow-up information on all participants and establishing and adhering to quality control measures to maintain high standards for data quality. The quality control procedures that have been developed and implemented for this study include following established procedures for the conduct of research and patient care at the University of Pittsburgh and University of Pittsburgh Medical Center (UPMC) in Pittsburgh, PA and at the Brooke Army Medical Center in San Antonio, Tx. Additionally, we will closely monitor data collection and form completion at both research sites.

All study staff will receive initial and ongoing training related to study procedures to maximize adherence to the protocol and to achieve high quality data.

Additionally, all study investigators and staff and the University of Pittsburgh will complete training as required, provided by the Collaborative Institutional Training

Institute (CITI) ([www.citi.pitt.edu](http://www.citi.pitt.edu)). The following training modules will be completed:

- Research Integrity
- Human Subjects Research
- HIPAA and
- Good Clinical Practice

All study investigators and staff at Brooke Army Medical Center will complete training as required, provided by the Collaborative Institutional Training Institute (CITI) (<https://www.citiprogram.org/default.asp>). The following training modules will be completed:

- Avoiding Group Harms: U.S. Research Perspectives
- Unanticipated Problems and Reporting Requirements in Biomedical Research
- Students in Research
- History and Ethical Principles
- Basic Institutional Review Board (IRB) Regulations and Review Process
- Informed Consent Social and Behavioral Research for Biomedical Researchers
- Records-Based Research
- Genetic Research in Human Populations
- Research With Protected Populations – Vulnerable Subjects: An Overview
- Vulnerable Subjects - Research Involving Prisoners
- Vulnerable Subjects - Research Involving Children
- Vulnerable Subjects - Research Involving Pregnant
- Women, Human Fetuses, and Neonates
- International Studies
- FDA-Regulated Research
- Human Subjects Research at the VA
- Research and HIPAA Privacy Protections

This research project is conducted by faculty and staff at the University of Pittsburgh and staff at the UPMC in facilities operated by the UPMC and University of Pittsburgh as well as by faculty and staff at Brooke Army Hospital. Investigators and study staff at the University of Pittsburgh and UPMC must adhere to the policies and procedures of the University of Pittsburgh, which can be found at <http://www.bc.pitt.edu/policies/>, and the UPMC, which can be found at <http://policymaterials.infonet.upmc.com/>. Additionally we strictly adhere to all University of Pittsburgh IRB policies and procedures, which can be found at <http://www.irb.pitt.edu/pandp/default.aspx>. Faculty and staff at Brooke Army Hospital must adhere to the policies and procedures of the Brooke Army Medical Center, which can be found at <http://fhpr.dhhq.health.mil/dmrn.aspx>.

## **11. Data Handling and Record-Keeping:**

### **11.1 Data recording/Case Report Forms**

A Case Report Form (CRF, see Appendix 1) will be completed for each subject enrolled into the clinical study. The Sponsor-Investigator will review, approve and sign/date each completed CRF; the Sponsor-Investigator's signature serving as attestation of the Sponsor-Investigator's responsibility for ensuring that all clinical and laboratory data entered on the CRF are complete, accurate and authentic.

*Source Data* are the clinical findings and observations, laboratory and test data, and other information contained in *Source Documents*. *Source Documents* are the original records (and certified copies of original records); including, but not limited to, hospital medical records, physician or office charts, physician or nursing notes, subject diaries or evaluation checklists, pharmacy dispensing records, recorded data from automated instruments, x-rays, etc. When applicable, information recorded on the CRF shall match the *Source Data* recorded on the *Source Documents*.

This study will utilize paper CRFs for study visits. These forms will include patient reported outcomes (demographics, Marx Activity Scale, and Cincinnati Occupational Rating Scale); vital signs, including blood pressure and heart rate; numerical pain rating scale; strength measurements and hamstring flexibility; medication logs; telephone follow-up logs, and any narrative notes written by the study staff. Study data will be recorded directly on these CRFs. The CRFs will be signed and dated by investigators and will serve as source documentation for this study.

The paper-based CRF will be created using word processing software but saved as .pdf files to prevent changes. The finalized forms will be marked as such by the generation of a unique form/screen identification number. Revisions to finalized forms and screens will not be encouraged once the study is underway. Reasons for revisions will be recorded and stored with the finalized versions of the forms and screens and all subsequent revisions. Dates of revisions will be recorded on the data collection forms as they occur. Forms with variable names and codes for the responses for each variable will be used to define all variables included in the study data set.

The following guidelines will be used to complete the study CRF:

- Forms will be completed legibly using black or blue ink;

- No participant identifiers will be recorded on patient questionnaires, with the exception of the Identification and Contact Information Form;
- Header information, including the participant identification number and date will be completed on all forms;
- If historical dates are required, the month/day/year should be provided. If the individual cannot recall the specific date of the month, the date should be set to the 15th of the month in which the event occurred;
- Abbreviations will not be used unless defined on the form;
- Responses should only be written in the spaces provided. Extraneous writing on the form should be avoided;
- To correct an error, a single line will be drawn through the error and the change will be dated and initialed by the individual that made the correction;
- When answering patient-reported forms, the Clinical Research Assistant will not help the subject answer the questions. Rather subjects will be instructed to answer all questions to the best of their ability. If the participant states they do not perform an activity and there is no opt out answer, the subject will be instructed to answer the question as if they were to do the activity;
- All questions should be answered. No questions should be left blank;
- If answers are illegible, every effort will be made to read the form. If possible, the participant will be contacted to answer the question or clarify the response;
- If data are not available to complete the form, the item for which the data is not available should be circled and the reason for the unavailability of data should be documented on the form near the appropriate field using the following conventions:
  - If the evaluation was not done, write “Not Done” or “ND” and provide a reason;
  - If the evaluation was done but the data is not available at the time the forms are being completed, indicate “Not Available” or “NAV” and document the reason, initial and date;
  - If an evaluation does not apply to the situation, indicate “Not Applicable” or “NA” and document the reason and initial and date;
- If an entire page is not complete, draw a diagonal line through the form & indicate “Not Done”, “Not Available”, or “Not Applicable” as appropriate along with the reason.

To ensure patient confidentiality, patient identifiers will not be written on the CRF at any time. Any list linking patient names to study identification numbers will be stored in locked file cabinets and /or on secure servers behind firewalls. All

paper based study documents will be stored in secure locked file cabinets. Any computerized records will be stored on secure servers behind firewalls.

